4.1.1 Feasibility endpoints

- 1) Number of eligible patients screened
- 2) Percentage of eligible patients consented
- 3) Number of patients randomised
- 4) Proportion to patients that complete the six-month follow-up

All the study endpoints for the clinical trial will be compared between CBD and the placebo groups at study end-point (visit 3/ day 182), adjusting for the baseline.

4.1.2 Primary endpoints

Severity of psychotic symptoms as measured using the CAARMS¹.

4.1.3 Secondary endpoints

Secondary clinical outcomes:

1) Distress associated with psychotic symptoms as measured using the CAARMS ¹ 2) Severity of anxiety symptoms assessed using the Hospital Anxiety and Depression Scale (HADS) ⁶¹ and in the level of global functioning (assessed using the social and role functioning scale) ⁶²

3) Clinical remission, as defined as no longer meeting the criteria for a diagnosis of CHR-APS

4) Total CAARMS score

5) Change (study endpoint minus baseline) in the severity of psychotic symptoms as measured using the CAARMS between the CBD and placebo groups

4.1.4 Safety endpoints

Incidence of adverse effects during the study period, assessed using the UKU sideeffect rating scale ⁶³

4.2 Trial Design

The viability of running the study will be evaluated with an internal pilot that will assess the ability of the study to identify, consent, randomise and follow up CHR-APS patients in the study.

We proposed a pragmatic, parrallel group, multicentre, blinded (participants, outcome assessor, chief investigator and statistician) randomised, placebo-controlled trial (RCT) of CBD versus placebo to reduce attenuated psychotic symptoms in CHR patients. Participants will be randomised to either 'Treatment as usual' (TAU) + Placebo; or TAU + Cannabidiol. We plan to recruit 300 patients, and randomisation will be in a 1:1 ratio. The allocation sequence will be generated by King's Clinical Trial Unit (KCTU) webbased system and concealed from all investigators.

4.3 Trial Flowchart

Outcome	Screening	0	1	2	3	4
Week No.	-1 to -3	1	4	13	26	30
			(±3day)	(±7days)	(±14days)	(±7days)
Informed Consent	X					
Socio-demographic	X					
Information						
Medical History	X					
Physical examination	X	Х			Х	
(Vital Signs, ECG)						
Urine Drug Abuse		Х	Х			
Screen						

AUDIT, FTND, CEQ, SDS	X				X	
TFLB		X	X		X	
Cannabinoid levels in blood to confirm use of or abstinence from cannabis		X	X	X	X	
Pregnancy Test	Х	Х	Х	X	X	
Screening Blood Sampling- Clinical laboratory (Haematology & Biochemistry)	X				X	
Concomitant	Х	Х	X	X	X	
Medication						
Study Exclusion criteria check	X	X				
NART	Х					
Adverse Events		Х	X	X	X	X
Randomisation		Х				
Study Medication Dispensing		X	X	X		
Study Medication Compliance (pill count)			X	X	X	
Compliance Blood Sampling (Cannabidiol levels)		X	X	X	X	
Comprehensive Assessment of At-Risk Mental State	X	X	X	X	X	
Hospital Anxiety Depression Scale		X	X	X	X	
Global Functioning (Social and Role scales)		X			X	
UKU Side Effect Rating Scale		X	X	X	X	

5 Participants

5.1 Selection of Participants

The proposed study will be a multi-centre study involving research-led early intervention services in the UK.

All centres will recruit patients into the internal pilot, that will progress to the RCT. Patients will be identified from early intervention (EI) teams linked to the recruitment hubs. Those participants recruited to the internal pilot will be included in the RCT. Patients who express an interest in the study and are identified as having CHR-APS by their clinical teams will be approached by study researchers and given a patient information sheet. Those who agree to take part in the study will be invited for a screening visit.

Heterogeneity in CHR: CHR patients are not a homogenous group and include three sub-groups of patients operationalised using standardized and internationally recognized criteria ('Comprehensive Assessment of At-Risk Mental States'; CAARMS) ¹ into: (i) those with 'attenuated psychotic symptoms' (APS), (ii) those with 'brief limited intermittent psychotic symptoms' (BLIPS) and (iii) a Vulnerability subgroup. Because the present study is primarily designed to assess the effect of CBD on the symptoms of CHR state, we will focus on the CHR-APS sub-group of patients and exclude the other two groups at the screening stage. This comprises the great majority (at least 80%) of CHR patients treated by NHS early intervention services ⁶⁴. Patients belonging to the other sub-groups have either minimal or only transient psychotic symptoms, and are often signposted to other mental health services or to primary care, as early intervention services typically prioritise care for CHR patients who are most symptomatic. A final consideration is that there is increasing evidence that the three CHR subgroups have distinct clinical outcomes, and may be biologically heterogenous ^{12,14 65,66}.

5.2 Inclusion Criteria

- Individuals (18-35 years) diagnosed with a clinical high-risk state (CHR) for psychosis, 'attenuated psychotic symptoms' sub-group (CHR-APS), as defined using CAARMS criteria ¹,

- To be able to understand and communicate in English,

- To be able to give informed consent.

5.3 Exclusion Criteria

- Lifetime history of a previous psychotic or manic episode lasting 7 days or longer,

- At screening, active suicidal ideation indicating significant current risk or past history of serious suicide attempt in the opinion of the principal investigator

- Lifetime neurological disorders (eg., epilepsy, excluding febrile convulsions) or severe intercurrent physical illness,

- Current treatment with psychotropic medication

- Lifetime treatment with antipsychotic medication for more than 7 days

- Poor premorbid/ preexisting functioning, as assessed with the National Adult Reading Test ⁶⁷, translated in an IQ<70

 Female patients who are pregnant, lactating or not using an accepatable effective form contraception if they are at risk of falling pregnant
 Taking part in another RCT

6 Interventions

6.1 Trial Medication

6.1.1 Investigational medicinal product

Cannabidiol (CBD; 600 mg/day) or matching placebo given in capsule form to be taken orally once a day around meal time.

Stephenson CBD Centre Ltd will supply the CBD and matching placebo capsules manufactured under good manufacturing practice conditions with appropriate certification.

Stephenson CBD Centre Ltd. Address: [name], United Kingdom Email: [contact]

The information presented on the labels for the CBD will comply with applicable national and local regulations.

6.1.2 Placebo

In order to guarantee masking, the placebo will be matched by color and size, not labelled, and consist of identical looking capsules manufactured and packaged by the same supplier in compliance with good manufacturing practice.

6.1.3 Dosing Regimen

For both the internal pilot and the RCT, the trial medication (CBD 600mg/day in capsule or matching placebo capsules) is to be taken once a day, after the first meal of the day, for a maximum of 182 days.

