3.2.2 Risks

A wealth of evidence also exists regarding the safety of CBD following both acute and longer-term dosing in humans. Doses up to 1500mg a day are well-tolerated, with no reported effects on physiological parameters such as heart rate, blood pressure or body temperature, no effect on gastrointestinal tract, psychomotor or psychological function other than mild sedation ³⁷. Orally administered CBD is subject to significant first pass metabolism following absorption with primary oxidation to an alcohol and a carboxylic acid, substantial excretion in faeces, then urine ⁵⁴, and an elimination half-life estimated at 2 to 5 days ⁵⁵. The 600 mg dose that we propose to use has previously been used in several acute and short-term studies, with minimal side effects ⁵⁶. In our proof-of-concept studies in CHR patients, CBD was tolerated as well as placebo, save for slightly more frequent reports of mild sedation. Published data from clinical trials in patients with acute psychosis ³⁵, epilepsy ⁵⁷ and neurodegenerative disease ⁵⁸, a case series for bipolar disorder (acute manic episode) ⁵⁹ and a survey of paediatric epilepsy ⁶⁰ indicate that CBD is much safer and better tolerated than antipsychotic medications.

3.3. Rationale for current study:

The rationale for the present study is to address a major unmet clinical need in CHR patients, the absence of an effective treatment for this group. We therefore plan to conduct a multi-site, double-blind, placebo-controlled RCT to evaluate the efficacy of CBD added to treatment as usual, to evaluate:

(iv) Its ability to alleviate psychotic and anxiety symptoms in CHR patients

- (v) Its safety and tolerability
- (vi) The neurochemical and neurophysiological basis of its effects

4 Trial Objectives and Design

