6.8 Subject Compliance

Compliance with CBD treatment will be assessed using pill-counts at visits 2, 3 and 4. Patients will be defined as complying in the presence of a pill count greater than 50% the expected number taken.

Furthermore, before the end of the study we will document a secondary measure of compliance by carrying out assay of CBD levels in blood at visits 1-4 in both arms of the study.

Patients who are defined as non-complying with the medication will be coded as protocol deviators.

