8.2.1 Primary Efficacy Parameters

Our primary efficacy parameter will be measured using the Comprehensive Assessment of At-Risk Mental States' (CAARMS)¹ (Monthly Version 2006). This is a validated instrument to rule out or confirm criteria for acute psychosis, map a range of psychopathology and functioning factors over time in young people at ultra high-risk of psychosis, and determine if an individual meets the criteria for an 'At Risk Mental State'. We will be using the English version in this population. The assessment has 7 subscales that target different areas of psychopathology and functioning: 1. Positive symptoms, 2. Cognitive change attention/concentration, 3. Emotional disturbance, 4. Negative symptoms, 5. Behavioural change, 6. Motor/physical changes, and 7. General psychopathology. Each subscale item is scored against (i) Severity (from 0 -never, absent – to 6 – extreme/psychotic/psychotic and severe –. Most items are also scored against (ii) Frequency and duration (from 0 – absent – to 6 – continuous) and (iii) Pattern of symptoms (from 0 – no relation to substance use noted – to 2 – noted only in relation to substance use). Moreover, a few items are additionally scored against (iv) Level of distress (from 0 to 100). Finally, the CAARMS includes: 8. Inclusion criteria for Group 1 Vulnerability group, Group 2 Attenuated psychosis group (CHR-APS), and Group 3 BLIPS group; 9. Psychosis threshold criterion (based on symptom severity, frequency,

and duration); and 10. Study withdrawal threshold criterion (based on Aggression/Dangerous Behaviour and/or Suicidality/Self Harm subscale severity) (Appendix 1). Within this instrument, lower scores are indicative of improved state, and higher scores of worsened state.

Primary clinical outcome: Severity of psychotic symptoms as measured using the CAARMS subscale Positive symptoms ¹. This subscale includes 4 items: 1. Unusual thought content, 2. Non-bizarre ideas, 3. Perceptual abnormalities, 4. Disorganised speech. Each subscale item is scored against (i) Severity (from 0 – never, absent – to 6 – psychotic/psychotic and severe –, (ii) Frequency and duration (from 0 – absent – to 6 – continuous), (iii) Pattern of symptoms (from 0 – no relation to substance use noted – to 2 – noted only in relation to substance use), and (iv) Level of distress (from 0 to 100). Within this instrument, lower scores are indicative of improved state, and higher scores of worsened state.

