8.4 Assessment of Safety

8.4.1 Specification, Timing and Recording of Safety Parameters

At screening the main safety measures will involve checking for study inclusion/ exclusion criteria, physical examination/ medical history/ safety blood investigations to ensure the absence of relevant disease or conditions that are a contraindication to participation in the study procedure as relevant. These will be repeated at Visit 3 or at withdrawal. Urine pregnancy test will be carried out at each visit for female participants. In the event of a positive test, the patient will be withdrawn from the study and their GP and mental health team informed. These are summarised in detail per visit below.

Screening Visit (Visit window -1): Medical History, Physical Examination (Vital signs, ECG), Pregnancy test (as appropriate), Clinical laboratory (Haematology: Full blood count and Haemoglobin; and Biochemistry: Urea & Electrolytes, liver function test, lipid profile).

Baseline Visit (Randomisation, on Day 0): Physical Examination (Vital signs, ECG), Pregnancy test (as appropriate), UKU Side-effect rating scale.

Month One Visit (Visit Window 1, at approximately Day 28): Pregnancy test (as

appropriate), AEs, UKU Side-effect rating scale.

Month Three Visit (Visit window 2, at approximately Day 91): Pregnancy test (as appropriate), AEs, UKU Side-effect rating scale.

Month Six Visit (Visit window 3, at approxiamtely Day 182): Physical Examination (Vital signs, ECG), Pregnancy test (as appropriate), Clinical laboratory (Haematology: Full blood count and Haemoglobin; and Biochemistry: Urea & Electrolytes, liver function test, lipid profile), AEs, UKU Side-effect rating scale.

Month Seven Final safety visit (Visit window 4, at approaximately Day 212): AEs/SAEs. This is going to be the final study visit.

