8.4.2.2 Anticipated Adverse events

In this population of CHR-APS, we anticipate:

1. AEs not related to the study intervention, not needing reporting:

- Worsening of psychotic symptoms, sleep disturbances, appetite disturbances, anxiety symptoms, mood symptoms, and suicidal ideation

- Transition to FEP

2. AEs potentially related to the study intervention, needing reporting:

- Hepatic Disorders (elevations of liver transaminases)

- Gastrointestinal Disorders (diarrhoea, gastroenteritis, abdominal pain, discomfort, weight decreased)

- Nervous System Disorders (somnolence, sedation, lethargy, fatigue, malaise, asthenia, drooling, salivary hypersecretion, gait disturbance)

- Infections (viral infections, pneumonia, fungal infections)

- Hypersensitivity Reactions (pruritus, erythema, rash, angioedema, hypoxia, respiratory failure)

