12.9.8 Per protocol population and analysis

We will carry out a complimentary secondary analysis of the primary outcome, using the per protocol population, this will exclude the set of patients that are coded as protocol violators. These will be due to: non-compliance; non-completion of instruments within the time-windows; non-compliance with the protocol in any other way.

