12.9.9 Subgroup analyses

The primary outcome will be split by the following subgroup: Time-window; sex; baseline severity; different levels of compliance; concomitant recreational cannabis use.

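### Dosing is capped at 182 days but the endpoint visit may fall as late as day 196, so a participant seen late but in window is assessed up to 14 days off drug

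*Protocol*

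**What the plan says.** Both the synopsis and section 6.1.3 cap treatment; the latter says the medication "is to be taken once a day, after the first meal of the day, for a maximum of 182 days". The flowchart (section 4.3) places visit 3 at week 26 with a tolerance of 14 days either side. Section 8.2 makes visit 3, nominally day 182, the time point for every efficacy comparison.

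Several measurements hang on that visit:

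- **Primary outcome.** The CAARMS is rated at visit 3. Section 8.2.1 specifies the "Monthly Version 2006".
- **CBD level.** The last blood sample in the flowchart is at visit 3. Section 6.8 describes a secondary compliance measure based on "carrying out assay of CBD levels in blood at visits 1-4 in both arms of the study"; that numbering fits the flowchart if baseline is counted as visit 1.
- **Laboratory tests and ECG.** Section 8.4.1 says of the screening safety checks: "These will be repeated at Visit 3 or at withdrawal". The flowchart shows neither at visits 1 or 2, and visit 4 is a records review for adverse events (section 7.5).

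Section 3.2.2 gives CBD "an elimination half-life estimated at 2 to 5 days". Section 12.9.8 lists "non-completion of instruments within the time-windows" among the reasons for exclusion from the per-protocol population, and section 12.9.11 takes the windows from the flowchart.

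**The concern.** A visit on day 190 follows the protocol in every respect and stays in the per-protocol set, yet it comes 8 days after the last permitted dose. The protocol asks what six months of CBD does, and for such participants the visit-3 measurements partly describe what happens after stopping.

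For efficacy, off-drug time enters the CBD arm only, so the comparison is pulled toward no difference. It cannot create a false benefit.

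For safety, section 8.4.2.2 names raised liver transaminases as an anticipated event potentially related to the drug. For a completer seen late, the only laboratory check scheduled after baseline would be taken off drug, and a change that reverses on stopping could be missed.

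For compliance, a fully adherent participant seen late would have a low CBD level that looks like poor adherence.

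**Working it through.** **Dates.** 26 × 7 = 182, so the window is 182 − 14 = 168 to 182 + 14 = 196. The longest gap after the last permitted dose is 196 − 182 = 14 days. It is 15 days if the first dose is taken on day 0, since 182 daily doses then end on day 181. Drug dispensed at visit 3 (section 7.4; the flowchart dispenses only at visits 0, 1 and 2) cannot cover the days before that visit.

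**Drug level at a late visit.** Fraction remaining = 2^(−gap/h), where h is the half-life of 2 to 5 days from section 3.2.2.

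| Visit day | Gap (days) | h = 2 | h = 5 |
|---|---|---|---|
| 190 | 8 | 2^(−4) = 0.063 | 2^(−1.6) = 0.330 |
| 196 | 14 | 2^(−7) = 0.008 | 2^(−2.8) = 0.144 |

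**The protocol's own power.** Section 10.2 plans 100 per arm for an effect of 0.40, two-sided t-test at 0.05. This gives power 0.804, which reproduces the stated 80%.

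**Primary outcome.** The protocol gives no share of late visits, so what follows is an illustration. Assumptions: the CAARMS looks back 30 days; lateness L is spread evenly over 0 to 14 days (mean 7); dosing stops at day 182; and the effect follows the drug level.

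- Residual effect-days after stopping = (h/ln 2)(1 − 2^(−L/h)). Averaged over L, this is 2.30 for h = 2 and 4.03 for h = 5.
- Share of the effect kept by an average late participant: (30 − 7 + 2.30)/30 = 0.843; (30 − 7 + 4.03)/30 = 0.901; with no residual drug counted, 23/30 = 0.767.
- Share kept at the extreme, day 196: (16 + 2.86)/30 = 0.63 to (16 + 6.18)/30 = 0.74.
- If a fraction f of visits is late and x is the share kept, the overall effect is 0.40 × (1 − f + f·x).

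| Share late | Residual drug | Effect | Power, 100 per arm |
|---|---|---|---|
| None | – | 0.400 | 0.804 |
| One quarter | h = 5 | 0.390 | 0.784 |
| One quarter | h = 2 | 0.384 | 0.772 |
| One half | h = 5 | 0.380 | 0.763 |
| One half | h = 2 | 0.369 | 0.737 |
| One half | none counted | 0.353 | 0.701 |

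**The case against.** The strongest reply is that a window centred on the nominal end of treatment is ordinary scheduling in a trial that calls itself pragmatic. The analysis is by intention to treat, participants who stop treatment remain on the assessment schedule, and so off-drug time in the primary comparison is already accepted. Up to two weeks in some participants is small beside that. This is fair for the primary outcome, and so are four related points:

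- The share of late visits is unknown. At 10% late, the same method leaves the effect at 0.39–0.40 and power at 79–80%.
- A six-month symptom effect need not fade in step with drug level. Any persistence shrinks the loss.
- The t-test ignores the baseline adjustment in section 12.9.5.1, which could raise power. The gain would be smaller if 0.40 already reflects change-score standard deviations, as the pilot data in section 10.2 suggest.
- The cap may mean days of dosing, not a calendar date, so a participant with missed doses might still be taking capsules after day 182.

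On the other measures, formal compliance rests on the pill count, CBD levels and the UKU side-effect scale are also collected at days 28 and 91, and a missed abnormality needs both a late visit and resolution within 14 days. Section 12.9.9 also plans a split: "The primary outcome will be split by the following subgroup: Time-window".

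These points limit the size of the problem without removing it. The days-of-dosing reading does not help a fully adherent participant. The time-window split could reveal a late-visit effect on the primary outcome but would not correct it, and it does nothing for the laboratory tests, ECG or CBD level. Nor do these points explain why an off-drug visit should count as per protocol.

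**Conclusion.** The concern holds. The dosing cap and the visit-3 window do not fit together, and a protocol-compliant visit can fall up to 14 days after the last permitted dose.

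The consequence is clearest for measures taken at a single moment. The CBD level rests only on the protocol's half-life and on dosing having stopped at day 182. The laboratory tests and ECG cannot be put back on treatment by any later analysis.

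For the primary outcome the effect is probably modest: a few points of power, about ten in the least favourable case shown. That size rests on an assumed share of late visits and on the effect tracking drug level. The bias is toward the null. The schedule should be corrected; the flaw does not undermine the trial's main comparison.

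**What to change.** Change the visit-3 window in the flowchart to −14/+0 days (day 168 to 182), so that the assessment is booked before dosing ends. Record the date of last dose at visit 3. Keep ratings made after day 182 in the main analysis, but treat them as out of window under sections 12.9.8 and 12.9.11. Interpret the visit-3 CBD level, laboratory tests and ECG against the last-dose date.

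The cost is one flowchart edit and one data field. The booking window is halved, so sites must book earlier. More visits will be labelled late and leave the per-protocol set, and some participants will be assessed before a full 182 days of exposure. The main estimate improves only as far as booking improves.

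Letting dosing continue until the visit-3 assessment would be more direct, but it raises the 182-day cap and the drug supply needed. Neither change adds an earlier laboratory test or ECG, since none is scheduled at visits 1 or 2.

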6.2 IMP Risks

IMP Risks, including safety data and overdose, are as documented in the Investigator brochure as well as in the Background & Rationale '3.2.2 Risks' subparagraph.

6.3 Drug Accountability

Only a study specific prescription can be used for dispensing/supplying study products. Only qualified physicians clearly given this role on the study delegation log can prescribe for the study, and only people designated again by the PI can collect medication (unless prior agreement that participants can collect themselves in which case ID is required). Only CBD supplied for this study can be dispensed against the study specific prescription. Full accountability records (recording the batch, expiry date and people dispensing or checking the prescription) will be completed. All prescriptions for both the CBD and Placebo will be dispensed and checked. All drug returns and empty packaging handed back to the pharmacy are recorded (quantity and date of return) and are held in a separate quarantine/drugs retuned area. Once medication has left the pharmacy it cannot under any circumstances be re-dispensed. Nothing is destroyed without the authorization from the PI and KHP-CTO CRA (destruction will be authorized on an ongoing basis).

